** 24-Hour Holter Monitor, 12-Lead EKG and Echocardiogram test results obtained within 60 days before informed consent and performed in accordance with the protocol, may be used for eligibility determination.

† Visits shall continue every 6 months until the PMA Supplement order has been issued by the FDA.

B. Anticipated Number of Sites and Subject Recruitment Rate

Up to 350 eligible subjects may be enrolled (providing consent and implanted). Eligible study participants may be enrolled from a maximum of 40 study sites in the United States.

C. Expected duration of subject participation

All eligible subjects will be asked to participate in the study until the PMA order has been issued by the FDA. Subjects can expect to participate for up to 2 years. The sequence and duration of specific study periods are described in **Table 1**.

D. Description of the Study “stopping rules” or “discontinuation criteria”

There shall be no stopping rules or discontinuation criteria. Enrollment into the Continued Access study shall end upon the issue of the PMA order by the FDA.

E. Accountability procedures for investigational products.

Clinical investigators will be trained in the importance of investigational products accountability. Impulse Dynamics will deliver OPTIMIZER Smart System related hardware to each enrolling clinical site, including the OPTIMIZER Smart IPGs, Chargers and an OMNI Smart Programmer. IPGs are generally not stored with the site inventory but rather carried in for each implant case by the engineer.

In accordance with 21 CFR 812.140, the clinical investigator is responsible for maintaining records of receipt, use or disposition of the investigational devices including:

- the type and quantity of the device, dates of receipt, and batch numbers or code marks
- names of all persons who received, used, or disposed of each device
- the number of units of the device returned to the sponsor, repaired, or otherwise disposed of, and the reason(s) therefore.

The IDE Device Accountability Log shall be maintained and updated throughout the study.

In accordance with 21§812.110, upon completion or termination of the clinical study or the investigator's part of the study or at Impulse Dynamic's request, the investigator shall return any remaining investigational product.

F. Data to be recorded directly onto CRFs and considered to be source data.

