In accordance with CFR 21 § 812.46, Impulse Dynamics will immediately conduct an evaluation of any UADE. If Impulse Dynamics determines that a UADE presents an unreasonable risk to subjects, it will terminate all investigations or parts of the investigations presenting that risk as soon as possible. Termination will occur no later than 5 working days after Impulse Dynamics makes this determination and no later than 15 working days after Impulse Dynamics first received notice of the effect.

VII. ASSESSMENT OF EFFECTIVENESS

Change in quality of life, as assessed by the Kansas City Cardiomyopathy Questionnaire.

VIII. ASSESSMENT OF SAFETY

Safety will be assessed by comparing the prevalence of mortality observed in the Continued Access Study (CAS) to the predicted probability of mortality derived from two validated heart failure models [MAGGIC (Meta-Analysis Global Group in Chronic Heart Failure) and SHFM (Seattle Heart Failure Model)]. The objective is to show that the observed prevalence of mortality is not worse than the derived predicted probability of mortality. Two pairwise comparisons (CAS vs. MAGGIC, CAS vs. SHFM) will be performed at 1 year and 3 years. Observed statistical differences will be noted if the two-sided p-value is less than 0.05.

A. Seattle Heart Failure Model (SHFM)

Specific baseline data will be collected in order to predict survival based on the SHFM. Computation of the SHFM score is done with 14 continuous variables and 10 categorical values; a web-based calculator is available to perform the calculation (<http://www.SeattleHeartFailureModel.org>).

B. Meta-Analysis Global Group in Chronic Heart Failure (MAGGIC)

Specific baseline data will be collected in order to predict survival based on the MAGGIC Prognostic Heart Failure Survival Model. The model identifies 13 independent predictors that should be routinely available although provisions have been made by the website (www.heartfailurerisk.org) for one or two variables to be unknown for an individual.

C. Censored and Missing Data

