In the SHFM and MAGGIC analyses above, subjects receiving an LVAD or heart transplant, cases of a device explants, and cases of a decision to permanently stop the therapy will be censored at the time of that change of therapy. These will be documented in the CRF, and will not be counted as an event. In any case of interim analysis, for the purpose of the Kaplan-Meier analysis, unless known otherwise, all cases that are under ongoing routine follow-up that have not yet completed the 3 years period shall be assumed to be alive and treated until the date of analysis.

Missing values may be overcome using imputation by the mean value of the cohort, or default values of the model for similar cohorts.

IX. OTHER ASSESSMENTS

Change in heart failure symptoms will be assessed using the NYHA classification assigned by a site clinician according to their standard clinical practice.

X. DIRECT ACCESS TO SOURCE/DATA DOCUMENTS

The investigators and institutions will permit trial-related monitoring, audits, IRB review, and regulatory inspections, providing direct access to source/data and regulatory documents.

XI. QUALITY CONTROL AND QUALITY ASSURANCE

Quality control and quality assurance is the responsibility of the Investigator and designated study staff. Impulse Dynamics clinical representatives will provide training and support to ensure that data quality is optimal (accurate, valid, reliable, complete and reported in a timely manner). Data will be monitored in accordance with Impulse Dynamic's Monitoring procedures. Data used for publication will not identify the subjects; publications will be generated in accordance with Impulse Dynamic's publication policy.

XII. ETHICS

Heart failure is a prevalent health problem throughout the world. Development of therapies to improve heart function to relieve symptoms, reduce hospitalizations and improve survival is a high priority in cardiovascular medicine.

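### Filling missing SHFM and MAGGIC inputs with a cohort mean or a model default can bias predicted mortality, the only safety comparator, and can make it depend on the fill used

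*Protocol*

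**What the plan says.** Section VIII sets the safety objective: "The objective is to show that the observed prevalence of mortality is not worse than the derived predicted probability of mortality". On the comparisons it says "Two pairwise comparisons (CAS vs. MAGGIC, CAS vs. SHFM) will be performed at 1 year and 3 years", and on the criterion, "Observed statistical differences will be noted if the two-sided p-value is less than 0.05". The study has one arm (section III), so the two predicted probabilities are the only yardstick for observed mortality.

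Section VIII.A says of the Seattle model: "Computation of the SHFM score is done with 14 continuous variables and 10 categorical values". Section VIII.B lists 13 predictors for MAGGIC and notes that the website allows "for one or two variables to be unknown for an individual".

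Section VIII.C, after the censoring rules for these two analyses, adds: "Missing values may be overcome using imputation by the mean value of the cohort, or default values of the model for similar cohorts". The sentence does not name the model inputs, but from its position that is what it most naturally covers. It does not say which fill applies to which variable or model.

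**The concern.** The protocol does state a rule here, and the rule is a weak method.

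- **Non-linearity.** Predicted mortality is a curved function of the inputs. Setting a missing value to the cohort mean removes that input's spread, and it ignores what the subject's other baseline values say about it.
- **Missingness related to risk.** If sicker subjects lack inputs more often, the mean makes them look healthier than they are and the benchmark falls.
- **Defaults.** A default taken from another cohort moves the prediction toward that cohort, up or down.
- **Categorical inputs.** A mean is not a category, and ten of the Seattle inputs are categorical.

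A benchmark that is too low makes it harder to show that mortality is not worse than predicted, and can create a false safety signal. A benchmark that is too high favours the device.

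**Working it through.** The protocol gives no expected mortality, margin, power or missing-data rate, so there is no figure of its own to reproduce. What follows is an illustration.

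**Inputs from the protocol.** The enrolment cap is 350 (section III.B). Annual mortality of roughly 20% in Class III (section I.E.1.a) is used for scale only.

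**Assumptions.** Mean 1-year risk is 10% or 20%. The input that may be missing has a log-hazard effect b of 0.2 or 0.4 per SD. The rest of the score has SD 0.6. The input is missing in 5% or 20% of subjects. A default lies 0.5 or 1 SD from the cohort mean.

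**Model.** Risk by year t = 1 − exp(−h·t·exp(b·x + o)). Here x is the standardised input, o is the rest of the score, and h is set so that mean 1-year risk is 10% or 20%.

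**Step 1: random missingness.** If a fraction m lacks x and receives the value d, the shift in mean predicted risk is m × [R(d) − R]. R is the mean risk with true values, and R(d) is the mean risk with x set to d for everyone. For 20% risk and b = 0.4, numerical integration gives:

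- mean fill: R(0) − R = 19.08 − 20.00 = −0.92, and 0.20 × (−0.92) = −0.18 (−0.19 by simulation);
- default 1 SD higher in risk: 0.20 × 6.63 = +1.33;
- default 1 SD lower in risk: 0.20 × (−6.60) = −1.32.

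**Step 2: all 1-year cases at 20% missing.** Shifts are in percentage points, from simulation of 1,000,000 subjects. The default columns and the first mean-fill column assume random missingness.

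| Risk | b | Mean fill, random | Mean fill, sicker more often missing | Default ±0.5 SD | Default ±1 SD |
|---|---|---|---|---|---|
| 10% | 0.2 | −0.03 | −0.50 | −0.21 / +0.16 | −0.37 / +0.37 |
| 10% | 0.4 | −0.12 | −1.08 | −0.44 / +0.26 | −0.71 / +0.71 |
| 20% | 0.2 | −0.05 | −0.91 | −0.37 / +0.30 | −0.68 / +0.68 |
| 20% | 0.4 | −0.19 | −1.93 | −0.79 / +0.52 | −1.32 / +1.33 |

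Under random missingness the shift is proportional to m, so at 5% missing it is a quarter of these. With sicker subjects more often missing, mean fill runs from −0.16 (5% missing) to −1.93 at 1 year. That column depends on how strongly missingness follows risk; a weaker link gives smaller shifts.

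**Step 3: several inputs.** With three inputs, each 20% missing at random and b = 0.3 per SD each, mean fill shifts the 1-year benchmark by −0.21 (10% risk) or −0.31 (20% risk). At 20% risk, defaults all 1 SD low or all 1 SD high give −2.86 or +3.12.

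**Step 4: scale.** The SE of an observed proportion is √(p(1 − p)/350). This is √(0.10 × 0.90/350) = 1.60 points at 10% and √(0.20 × 0.80/350) = 2.14 points at 20%. In the last row of the table, under random missingness, mean fill and a default 1 SD higher differ by 1.33 − (−0.19) = 1.52 points, or 1.52/2.14 = 0.71 SE.

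**Step 5: effect on the comparison.** Take true mortality of 20%, a fixed benchmark B, and a difference noted when the observed proportion is more than 1.96 × √(B(1 − B)/350) from B.

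- B = 20%: 2.5% chance of being noted as worse, and 2.5% as better.
- B = 18%: the upper limit is 18 + 1.96 × 2.05 = 22.0, z = (22.0 − 20)/2.14 ≈ 0.95, and the chance of worse is 17%.
- B = 22%: the chance of worse is 0.15%, and of better 14%.
- B = 19.9% or 20.1%: the chance of worse is 2.8% or 2.2%, almost no change.

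A 2-point move lies at or beyond the edge of the one-input cases in the table. An upward move of that size needs several inputs with defaults in the same direction.

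**The case against.** The strongest reply is that little will be missing. Six laboratory analytes are scheduled for every subject at baseline (Table 1, section V.B), and results up to 30 days old are accepted. An investigator may end the participation of a subject who cannot complete the baseline assessments (section IV.C). Ejection fraction, NYHA class and QRS width decide eligibility, and Appendix C lists baseline forms for demographics, medications, laboratory values and cardiac devices. This largely stands and is why the severity is not higher. It is not complete: the Seattle score needs 24 inputs, ending participation is discretionary, and sections VIII.B and VIII.C themselves provide for missing values.

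A second reply is that mean fill errs against the device. That also stands: it lowered the benchmark in every scenario run. It does not cover defaults, which can move the benchmark either way.

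A third is that the sentence can be read as a mean where a mean makes sense and a default elsewhere. That is possible, but the text does not say so.

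A reader might infer more than the protocol supports:

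- **That the benchmark is biased as a matter of fact.** The amount and mechanism of missingness and the default values are not given.
- **That the fill will be chosen once deaths are known.** A statistical analysis plan, not at hand, may fix it beforehand.
- **That MAGGIC has a third, conflicting method.** The website's allowance for unknowns may simply be the model default that section VIII.C means.

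**Conclusion.** The point holds in a limited form. Section VIII.C authorises two single fills that ignore the subject's other data, one of them unsuited to categorical inputs, for the only comparator of the safety objective. Predicted mortality can therefore be biased and can differ with the fill.

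Under the assumptions above, mean fill with random missingness is close to harmless: up to about 0.2 points at 1 year for one input and 0.3 for three. The effect becomes comparable to the standard error of about 1.6 to 2.1 points only when missingness is substantial and either follows risk or is filled with defaults well away from this cohort. The protocol neither shows nor excludes that situation. Severity is low to moderate, and this is a cheap improvement.

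**What to change.** Replace the sentence in section VIII.C so that:

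1. missing Seattle and MAGGIC inputs are multiply imputed from the collected baseline variables, with logistic or ordinal models for categorical inputs;
2. predictions are averaged over the imputed sets;
3. the method is fixed before mortality is compared with the predictions;
4. the comparison is repeated with model defaults, including the MAGGIC website's handling of unknowns, as a sensitivity analysis;
5. the number missing is reported for each input.

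Multiple imputation uses the subject's other data, but it is not a cure if missingness depends on the unmeasured value itself. Items 4 and 5 let the reader judge that risk.

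The cost is a short text change and modest programming, because scores must be computed by formula for each imputed set instead of once by web calculator. No new data are needed.

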APPENDIX C

Case Report Form Listing for the FIX-HF-5CA Study

Data for this study will be recorded into data entry screens using the Clindex electronic data capture (EDC) system. The following is a list of the electronic Case Report Forms:

Screening and Baseline Forms:

- Demographics
- Medical History and Risk Factors
- Physical and Assessments
- Medications
- Baseline Laboratory Values
- NYHA Classification
- Kansas City Cardiomyopathy Questionnaire
- Concomitant Cardiac Devices
- Eligibility Determination

Optimizer Index Procedure Information

- Intraoperative Event(s)
- OPTIMIZER Smart Subject Training
- Discharge

Optimizer Revision/Replacement/Removal Procedure

- Intraoperative Event(s)

Follow-up Assessment Forms:

- OPTIMIZER Interrogation
- Physical and Assessments
- Medications
- Kansas City Cardiomyopathy Questionnaire

Miscellaneous Forms

- End of Study/Withdrawal
- Protocol Deviation

Safety Event Forms

- Adverse Event Form
- Hospitalization Log
- Mortality Form

APPENDIX D

Device-device Interaction Testing Procedure

Subjects that have a concomitant device (e.g., ICD, pacemaker) will undergo additional testing at the end of the implant procedure to ensure appropriate function of both the Optimizer Smart System and the concomitant device. The following steps summarize the required testing:

1. Program the ICD so that it does not deliver antitachycardia therapy during this test.
2. Program the sensing windows of the Optimizer IPG and ensure that it can be programmed to consistently delivery CCM therapy in the presence of the concomitant device.
3. Activate CCM therapy and evaluate the real-time intracardiac electrograms and marker channels to ensure that CCM therapy does not cause inappropriate oversensing or undersensing during normal sinus rhythm that cannot be resolved through reprogramming or lead repositioning.
4. While CCM therapy is being delivered, ensure that CCM therapy does not cause inappropriate inhibition of bradycardia pacing. In patients that require bradycardia pacing, activate CCM therapy during pacing and evaluate the real-time intracardiac electrograms and marker channels to ensure that CCM therapy does not cause inappropriate inhibition of bradycardia pacing therapy that cannot be resolved through reprogramming or lead repositioning.
5. At the implanting physician's discretion, program the ICD to detect and convert an induced ventricular tachyarrhythmia. Program the Optimizer Smart to deliver continuous CCM therapy. While CCM therapy is being delivered, induce VT/VF and ensure that the implanted ICD can appropriately detect the ventricular tachyarrhythmia. Ensure that CCM therapy does not cause inappropriate undersensing during VT/VF that cannot be resolved through reprogramming or lead repositioning.
